9.3.3. Key Secondary Efficacy Estimand Analysis

9.3.3.1. WIN Ratio

Question of Interest	To assess the efficacy of treatment with dronedarone on top of usual care versus usual care on adverse outcomes in patients with first-detected AF.
Objective Description / Study Population	Key secondary objective of the study / All randomized participants
Endpoint	Multivariate endpoint consisting of the measures listed in Table 2
Intercurrent Events	All other intercurrent events will be ignored in these analyses.
Population Summary	WIN ratio estimate. Values above 1.0 suggest benefit from the treatment with dronedarone and usual care versus usual care alone

Unmatched WIN ratio model according to Finkelstein and Schoenfeld method (1999) compares every patient on the dronedarone arm with every patient in the usual care arm, noting ‘winner’, ‘loser’, or ‘tied’ for each comparison. For each pair, the component outcomes will be compared in descending order of importance until one of the patients in the pair demonstrates a better outcome compared with the other. The hierarchy of component outcomes are shown in **Table 2**. For example, the dronedarone arm is a ‘winner’ or ‘loser’ according to who had an all-cause death first. If that is unknown, then whether they are labelled a ‘winner’ or ‘loser’ depends on who had an ischemic stroke or systemic embolism first, except all-cause mortality. In a similar way using the rest of hierarchy of outcomes, decide a ‘winner’ or ‘loser’. Otherwise, they are considered tied. The win ratio is the total number of dronedarone arm winners divided by the total number of dronedarone arm losers. A 95% CI and P-value will be obtained by Luo’s method (2015).⁶⁴ Statistical significance will be determined using the multiplicity adjustment methods described below in **Table 4**.

9.3.3.2. Cardiovascular Hospitalization

Question of Interest	To assess the efficacy of treatment with dronedarone on top of usual care versus usual care on the rate of first occurrence of unplanned cardiovascular hospitalization in patients with first-detected AF.
Objective Description / Study Population	Key secondary objective of the study / All randomized participants
Endpoint	Main analysis: Time from randomization to the first occurrence of unplanned cardiovascular hospitalization within 12 months of randomization. Exploratory analysis: Overall rate of all recurrent cardiovascular hospitalization events within 12 months of randomization.
Intercurrent Events	Death – follow-up will be censored at date of death. Hazard ratio for cardiovascular hospitalization will be estimated among participants still alive and in follow-up. Early study withdrawal or lost-to-follow-up – follow-up will be censored at the last date when patient event status was known. Analysis will assume that censoring is non-informative. All other intercurrent events will be ignored in these analyses.
Population Summary	Main analysis: Hazard ratio estimate based on a Cox proportional hazards model for time to first event. Exploratory analysis: Hazard ratio estimate based on a proportional intensity model developed by Anderson & Gill (1982) using all recurrent events. Hazard Ratio values below 1.0 suggest benefit from the treatment with dronedarone and usual care versus usual care alone

For the main analysis the Cox proportional hazards model will be fit for time to first event with the treatment group as exposure variable. Follow-up will be censored early if death occurs prior to cardiovascular hospitalization. The treatment effect will be presented as a cause-specific hazard ratio (dronedarone on top of usual care vs. usual care) and a nominal 95% CI.

For the exploratory analysis a generalization of the Cox model to handle recurrent events, developed by Anderson & Gill (1982), with robust standard errors to account for individual patients' heterogeneity. Even though the Anderson-Gill approach assumes independence between all observed event times irrespective whether these event times correspond to the same patient or to different patients, this approach will be the analysis method for the total number of events of cardiovascular hospitalization. The treatment effect will be presented as a hazard ratio (dronedarone on top of usual care vs. usual care) and a nominal 95% CI.

9.3.3.3. All-cause Mortality

Question of Interest	To assess the efficacy of treatment with dronedarone on top of usual care versus usual care on the rate of all-cause mortality in patients with first-detected atrial fibrillation
Objective Description / Study Population	Key secondary objective of the study / All randomized participants
Endpoint	Time from randomization to death within 12 months of randomization
Intercurrent Events	Early study withdrawal or lost-to-follow-up – follow-up will be censored at the last date when patient event status was known. Analysis will assume that censoring is non-informative. All other intercurrent events will be ignored in these analyses.
Population Summary	Hazard ratio estimate based on a Cox proportional hazards model. Values below 1.0 suggest benefit from the treatment with dronedarone and usual care versus usual care alone

The Cox proportional hazards model will be fit for time to death with the treatment group as exposure variable. The treatment effect will be presented as a hazard ratio (dronedarone and usual care vs. usual care) and a nominal 95% CI.

9.3.4. Tertiary Efficacy Endpoints Analysis

Analysis methods for the tertiary efficacy endpoints will be provided in the statistical analysis plan.

9.3.5. Patient reported outcomes (12-month change in quality of life)

Question of Interest	To estimate the effect of treatment with dronedarone versus usual care on 12-month change in patient reported quality of life in patients with first-detected AF.
Objective Description / Study Population	Patient reported outcomes study / All randomized participants who did not die during follow-up
Endpoints	12-month change in quality of life compared to baseline, assessed by AFEQT Overall Score and by MAFSI Total Severity score.

Intercurrent Events	
Death – 12-month change in quality of life will be assessed in participants who were alive at the 12-month follow-up assessment.
 
Early study withdrawal, lost-to-follow-up, or missing assessment – analysis will assume that missing data due to withdrawal, lost-to-follow-up or other reasons is not informative conditional on patient demographics, heart failure status, time since AF diagnosis, and baseline value of quality of life assessments. Analysis will adjust for missing data using inverse probability weighting.

Population Summary	
Difference in mean change from baseline between dronedarone versus usual care, estimated using analysis of covariance. For the AFEQT, a mean difference greater than zero suggests benefit from treatment with dronedarone versus usual care alone. For the MAFSI, a mean difference less than zero suggests benefit from treatment with dronedarone versus usual care alone.

This objective will be assessed using Analysis of Covariance (ANCOVA) with the 12-month change in quality of life (12-month score – baseline score) as response variable, treatment group as exposure, and baseline score as covariates. Inverse probability weighting will be used to adjust for missing data. The treatment effect will be presented as the difference between mean 12-month change (dronedarone and usual care vs. usual care) and a nominal 95% CI.

9.3.6. Safety Analyses

All safety analysis will be performed in the on-treatment (OT) population during the on-treatment period. A linearized event rate for each safety endpoint (see Section 8.2) for each treatment group will be calculated as percentage per patient year, and the approximate 95% CI for the difference of linearized event rates will be calculated as

$$\left(\frac{r_D}{T_D} - \frac{r_U}{T_U}\right) \pm 1.96 \sqrt{\frac{r_D}{T_D^2} + \frac{r_U}{T_U^2}}$$

where subscript D and U denote the dronedarone and usual care arms, respectively, and r is the total number of occurrences of the safety outcome, and T is the total patient time (years).⁶⁵

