The study intervention will be treatment with oral dronedarone 400 mg twice daily in addition to usual care. The comparator arm will be usual care alone. Usual care will be defined as best-practice, guideline-directed therapy of AF, including but not limited to (a) stroke prevention therapy, (b) rate-control, and (c) treatment of risk factors. More specifically, oral anticoagulation in those men with a CHA₂DS₋₂VASc score of 2 or greater or women with a CHA₂DS₋₂VASc score of 3 or greater, rate control, and treatment of concomitant cardiovascular conditions (e.g. coronary artery disease or heart failure) will be required in all trial participants. As defined in the protocol, those randomized to the dronedarone arm will be prescribed 400 mg oral dronedarone twice daily. Similar to the approach in the EAST trial, those randomized to usual care alone will initially be treated without rhythm-control therapy¹⁴, however rhythm-control therapy (except dronedarone) may be initiated during follow-up in the usual care arm to ameliorate AF-related symptoms despite adequate rate-control therapy per current guideline recommendations. In the dronedarone arm concomitant digoxin use is contraindicated due to P-gp interaction based upon data from the PALLAS trial.²⁹

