6.3. Concomitant Treatment

Concomitant drug therapy will be recorded in the case report form at baseline and all follow-up periods. In the dronedarone arm concomitant digoxin use is contraindicated due to P-gp interaction based upon data from the PALLAS trial.²⁹ Observational data have observed a small increased risk of bleeding in patients treated with dronedarone and direct acting oral anticoagulants, however, there is no apparent increased risk of intracranial bleeding.⁶⁰

Cardioversion (pharmacologic or electrical) is not an exclusion and is permitted throughout the trial. Patients who are planned or scheduled to undergo catheter ablation during screening or at the baseline visit are not eligible. Following enrollment, if a patient experiences escalation of symptoms or refractory symptoms, escalation of rhythm control interventions, including catheter ablation, can be considered if deemed necessary by the patient's treating physician.

7. Discontinuation of Study Intervention and Participant Discontinuation/Withdrawal

The end of the study is defined as the date of the last visit of the last participant in the study or last scheduled procedure shown in the schedule of activities for the last participant in the study. A participant is considered to have completed the study if he/she has completed all periods of the study including the last study visit at 12 months, or if deceased during the follow-up period.

Patients should not be discontinued when they experience a primary endpoint event. They should continue in the trial until the end of study visit at the end of follow-up. The study intervention therapy should be continued unless deemed otherwise by the treating physician or if the patient requires initiation of a different antiarrhythmic medication.

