7.1. Discontinuation of Study Intervention

In rare instances, it may be necessary for a participant to permanently discontinue study intervention. If study intervention is permanently discontinued, the participant will remain in the study until they complete 12-month follow-up/final visit.

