9.2. Analysis Sets

Population	Description
Intent-to-treat (ITT)	
 • All randomized participants will be included in the analyses according to the intervention arm they were assigned,

Population	Description
	regardless of treatment initiation, discontinuation or switching.
On treatment population and on-treatment period	
 All randomized participants who took the assigned treatment will be included in the analyses according to the intervention arm they were assigned until they switch or discontinue the assigned treatment regimen. Follow-up will be censored 5 days after treatment switching or discontinuation, i.e. all events occurring until 5 days after discontinuation or switching to the other treatment group will be attributed to the randomized group and all events occurring later than 5 days after discontinuation or switching will be censored. Participants in the usual care arm who start dronedarone drug therapy will be considered to have switched treatment regimen. Participants in the dronedarone arm who temporarily suspend or are non-adherent with dronedarone for >14 consecutive days will be considered to have discontinued treatment.

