9.3.7. Other Analyses

On treatment analysis of efficacy endpoints

As sensitivity analyses, the primary and key secondary objectives will be tested using the OT population during the on-treatment period.

Pre-Specified Subgroups of Interest

Subgroup analyses for the primary outcome will be performed to assess whether the therapeutic effect is consistent across all patients, or whether it varies according to specific patient

characteristics. These analyses will focus on whether the relative therapeutic effect differs according to the following baseline variables:

- Age (<70 years vs. ≥70 years)
- Sex (male vs. female)
- Race (white vs. racial minorities)
- AF type (paroxysmal vs. persistent, or long-standing persistent)
- Left atrial dimension (<50 mm versus ≥50 mm)
- AF duration (<30 days versus ≥30 days)
- Structural heart disease (present vs. absent)
- Hypertension (present vs. absent)
- Chronic kidney disease (estimated eGFR ≤60 vs. >60 ml/min)
- CHA₂DS₂-VASc score (0-1 vs. ≥2 excluding sex)
- Sleep Apnea (present vs. absent)
- BMI (<30 vs. ≥30)
- Heart failure vs no heart failure
- Left ventricular ejection fraction (LVEF) (41-55 vs. >55)
- Recent hospitalization for AF vs None

Cox proportional hazards regression modeling will be used to assess whether treatment effect is heterogeneous across pre-specified subgroups. For each subgroup analysis, the Cox proportional hazards model will be fit for time to first event including the subgroup as a stratification factor, and the treatment group and interaction between treatment and subgroup as covariates. The treatment effect within each subgroup level will be presented as a hazard ratio (dronedaron on top of usual care vs. usual care) and a 95% CI. Heterogeneity will be assessed by presenting the interaction P-value, using a two-sided test.

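### On-treatment is the only stated safety analysis, and its censoring triggers differ between the arms, so events after stopping or resuming are left out almost only in the dronedarone arm

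*Protocol*

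**What the plan says.** Section 9.3.6 (Safety Analyses) fixes both the population and the period: "All safety analysis will be performed in the on-treatment (OT) population during the on-treatment period". It compares event rates per patient-year, that is, total occurrences divided by total patient time in each arm.

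Section 9.2 (Analysis Sets) defines the on-treatment period. The set holds randomised participants who took their assigned treatment. "Follow-up will be censored 5 days after treatment switching or discontinuation". The triggers are arm-specific:

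- Dronedarone: "Participants in the dronedarone arm who temporarily suspend or are non-adherent with dronedarone for >14 consecutive days will be considered to have discontinued treatment".
- Usual care: "Participants in the usual care arm who start dronedarone drug therapy will be considered to have switched treatment regimen".

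Three other places bear on how this works:

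- Section 6, opening text: "rhythm-control therapy (except dronedarone) may be initiated during follow-up in the usual care arm".
- Section 7, opening text: "The study intervention therapy should be continued unless deemed otherwise by the treating physician or if the patient requires initiation of a different antiarrhythmic medication".
- Section 7.1: "If study intervention is permanently discontinued, the participant will remain in the study until they complete 12-month follow-up/final visit".

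Section 9.3.7 uses the same set as a sensitivity analysis for efficacy, in which "the primary and key secondary objectives will be tested using the OT population during the on-treatment period".

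**The concern.** A safety comparison between randomised arms is easiest to interpret when an event counts on the same terms in both. Here the observation window closes for many ordinary reasons in one arm and for one rare reason in the other. Two kinds of event drop out:

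- an event that first appears more than 5 days after dronedarone is stopped;
- an event in a patient who paused for more than 14 days and is back on the drug.

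Section 2.2.1 names hepatic injury and heart failure exacerbation as known risks. Table 3 adds atrioventricular block, QT prolongation and ventricular arrhythmia. If some patients stop because of early signs of such harm, part of the harm may surface after the window has closed. Censoring would then be informative, and mainly in one arm. The same applies to the on-treatment efficacy analysis.

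**Working it through.** **Step 1. The triggers side by side.**

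| Course of events | Dronedarone arm | Usual-care arm |
|---|---|---|
| Never takes assigned treatment | Not in the set (9.2) | Hardly applies in practice |
| Stops for any reason | Censored 5 days later (9.2) | No corresponding trigger |
| Gap of more than 14 days, then resumes | Treated as discontinued; no re-entry stated (9.2) | No corresponding trigger |
| Needs another antiarrhythmic | A stated reason not to continue dronedarone (7), hence censored | Permitted (6), not listed as a switch (9.2), stays in |
| Starts dronedarone | Not applicable | Censored 5 days later (9.2), but not a permitted option (6) |

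The fourth row needs no assumption: the same clinical course with the same second drug is cut short in one arm and followed in the other. Section 7.1 keeps patients who stop in the study to 12 months, so the omitted events can be captured. Section 9.2 does not say whether the 5 days run from the last dose or from the end of the 14-day gap.

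**Step 2. What the protocol quantifies.** It gives no discontinuation rate and no safety precision. Its main design figure reproduces: with 733 events and HR 0.79, z = √(733/4) × |ln 0.79| − 1.96 = 3.19 − 1.96 = 1.23, so power is 0.891 against 0.89 in Table 5. Nothing below depends on it.

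**Step 3. Direction of the effect on the rate.** Let λ be the usual-care rate, f the share of dronedarone-arm person-time that is on-treatment, R the on-drug rate ratio and Q the rate ratio after the window closes.

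- On-treatment difference: λ(R − 1)
- Full-follow-up difference: λ[fR + (1 − f)Q − 1]
- Full minus on-treatment: λ(1 − f)(Q − R)

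The on-treatment rate difference is smaller than the full-follow-up one only if Q > R. It is equal if Q = R and larger if Q < R.

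**Step 4. Illustration; all rates are assumptions.** Take 1500 per arm (Section 9.5), one year each with no attrition, λ = 3 per 100 patient-years, R = 2, and exponential discontinuation with proportion d by 12 months. With k = −ln(1 − d) and L = 5/365, f = L + [1 − e^(−k(1−L))]/k. For d = 20%, k = 0.223 and f = 0.899. On-treatment events are 1500 × 0.899 × 0.06 = 80.9. Omitted events are 1500 × 0.101 × 0.03 × Q, which is 4.5, 9.1 or 13.6 for Q = 1, 2 or 3.

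| d | f | Share of dronedarone-arm events omitted, Q = 1 / 2 / 3 | Full-follow-up difference per 100 patient-years, Q = 1 / 2 / 3 |
|---|---|---|---|
| 10% | 0.950 | 2.5% / 5.0% / 7.2% | 2.85 / 3.00 / 3.15 |
| 20% | 0.899 | 5.3% / 10.1% / 14.4% | 2.70 / 3.00 / 3.30 |
| 30% | 0.845 | 8.4% / 15.5% / 21.6% | 2.54 / 3.00 / 3.46 |
| 40% | 0.788 | 11.8% / 21.2% / 28.7% | 2.37 / 3.00 / 3.63 |

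The on-treatment difference is 3.00 in every row. With an assumed 1% crossover, f in usual care is 0.995.

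**Step 5. On-treatment efficacy; also assumption-based.** Suppose no drug effect, the 10/20/25/30% event curve of Section 9.5, 20% attrition and 20% stopping. The table gives the dronedarone-arm event rate per patient-year, on-treatment divided by full follow-up, when stopping coincides with a lasting rise in hazard of 1.5-fold or 2-fold.

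| Share of stops at a deterioration | 1.5-fold | 2-fold |
|---|---|---|
| All | 0.97 | 0.94 |
| Half | 0.99 | 0.98 |
| A quarter | 1.00 | 0.99 |
| None | 1.01 | 1.01 |

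The tilt towards benefit comes from the assumed share of informative stops, which the protocol does not give.

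**The case against.** The case for leaving the plan alone has substance. An on-treatment safety set is a common choice, and it matches Section 9.1, which words the safety objective around patients taking dronedarone. Section 7.1 calls permanent discontinuation rare. An event that itself causes stopping occurs before the window closes and is counted. Serious harms also reach all-randomised comparisons: all-cause mortality is analysed that way, and the primary endpoint includes unplanned admission for heart failure, ventricular arrhythmia, pacemaker implantation and major bleeding. The data and safety monitoring board's review (Section 9.4) is not stated to be limited to on-treatment data. Further tables could appear in the SAP.

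Most of this stands and limits the point. It does not remove it. Section 9.3.6 says all safety analysis, which is a commitment and not a detail left open. The efficacy endpoints give no full-follow-up comparison of hepatic injury, atrioventricular block, QT prolongation or rash as safety events. Nor does the stated objective explain why on-drug events after a resumed interruption should be excluded.

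Three stronger readings are tempting and not supported:

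- **Only dronedarone patients are censored.** Section 9.2 also censors usual-care patients who start dronedarone, and in the dronedarone arm only gaps of more than 14 consecutive days count.
- **Drug harms are necessarily understated.** Late events are missing from the counts, but the analysed quantity is a rate, and Step 3 shows that it can move either way.
- **The trial's false-positive risk is inflated.** Section 9.1.1 restricts formal testing to the primary objective and the win ratio, both analysed in all randomised participants. The on-treatment efficacy analysis is a sensitivity analysis and carries no alpha.

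**Conclusion.** The point holds as a design weakness of moderate weight, below a must-fix. From the text alone: on-treatment is the only stated safety analysis; its triggers are unequal in practice; there is no re-entry rule; and events more than 5 days after stopping, or after resumption, are left out almost only in the dronedarone arm although those patients are followed to 12 months.

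The direction and size of bias in the per-patient-year rate cannot be determined from the protocol. Under the Step 4 assumptions, 2.5% to 29% of dronedarone-arm events are omitted, and the full-follow-up rate difference lies between 0.63 below and 0.63 above the on-treatment figure of 3.00 per 100 patient-years. Harm is understated where risk after stopping exceeds on-drug risk, as with delayed injury or stopping at early signs. The efficacy figures in Step 5 are illustration only.

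**What to change.** 1. In Section 9.3.6, add a safety analysis of all randomised participants by assigned arm through 12 months, reported alongside the on-treatment analysis. Which of the two is called the main analysis is a matter of preference.
2. In Section 9.2, count person-time and events after resumption as on-treatment.
3. In Section 9.2, state whether the 5 days run from the last dose or from the end of the 14-day gap.
4. In Section 9.3.7, describe the on-treatment efficacy analysis as supplementary and subject to informative censoring.

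A longer window after stopping, or weighting for censoring, could be considered, but the point does not depend on either.

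The cost is wording and one more set of tables, since Section 7.1 already keeps these patients in follow-up. All-randomised rates may be diluted by time off the drug; presenting both analyses lets the reader see this.
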